3.2 EXPLORATORY EFFICACY ENDPOINTS

1. Anterior Chamber Cell count on slit lamp biomicroscopy. ██████████
2. Anterior chamber flare
3. Subject-rated ocular pain assessment

3.3 DESCRIPTION OF THE STUDY DESIGN

This is a Phase I/IIa Multicenter, Double-Masked, Randomized, Vehicle-Controlled, Dose-ranging study designed to evaluate the safety and preliminary efficacy of TRS01 eye drops at three dose levels compared to vehicle in subjects with post-surgical inflammation.

Approximately 60 subjects with ocular inflammation following cataract surgery will be randomized at approximately five centers, in the USA and in France.

Subjects who provide informed consent and meet all study randomization criteria will be enrolled in the study and randomized in a 1:1:1:1 ratio to receive TRS01-█%, TRS01-█, TRS01-█% or vehicle eye drops four times daily.

The eye that underwent cataract surgery is defined as the study eye. TRS01 should not be administered in the fellow eye.

Treatment assignments will be masked to Tarsius, study subjects, Investigators, and site staff. In order to prevent unmasking, all study medications during the Treatment Period will be supplied in identical packages.

The study design includes 14-days of a double-masked treatment period, with the endpoint assessment conducted on Day 15 (FIGURE 1 summarizes the study phases, anticipated visits and number of subjects at each phase and Appendix 1 summarizes the schedule of assessments from Screening through Day 15).

Randomization is employed as an unbiased method of assigning subjects to four groups in equal allocation.

Male and female subjects aged 18 or older and 1-day post cataract surgery with anterior chamber cells \geq grade 2 in the study eye, are eligible to be randomized to participate in the treatment phase of the study.

[figure not shown]
Double-masked eye drops will be administered four times daily from Day 1 through Day 14 by the study participant (or care provider) to the study eye. The safety endpoint is on Day 15. Exploratory efficacy measurements will be collected.

Visits (including the surgery day):

1. Visit 1/Days -30 to -1 – Screening: Initial screening for eligibility – 1-30 days before the surgery.
2. Visit 2/Day 0 – Surgery: Eligible subjects will undergo routine cataract surgery according to investigator's standard procedures. No steroid or NSAID will be given before, during or after the surgery. Acetaminophen on the day of surgery is allowed.
3. Visit 3/Day 1 – Randomization: Subjects who meet the post-surgery qualification criteria of \geq grade 2 anterior chamber cells in the study eye will be randomized and will initiate dosing with IP. The subject's first dose will occur after randomization under the observation of an Unmasked staff member.
 - 3.1. 40 minutes \pm 10 minutes post first dose, AEs, if any, will be recorded. Changes that are expected due to uncomplicated cataract surgery (such as discomfort, scratchy feeling, significant brightness, changes in the perception of the operated eye, corneal edema) will be collected, but will not be classified as AEs. Subjects will be given one bottle of IP and instructed to dose three more times that day and to begin dosing four times a day on the following day and onward.

4. Visit 4/Day 3: Evaluation
5. Visit 5/ Day 8: Evaluation and replacement of IP.
6. Visit 6/ Day 15: Evaluation, collection of IP and study completion.

FIGURE 1: STUDY VISITS

Please note that both eyes cannot be part of the study – there should be a treated eye (study eye) and an untreated eye (non-study eye). The non-study eye should not undergo any surgical procedure during the trial.

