3.1 SAFETY ENDPOINTS

The primary safety parameter in this study is the incidence and severity of treatment-emergent and treatment-related adverse events (AEs), both systemic and ocular events in subjects with post-cataract inflammation. Changes that are expected due to uncomplicated cataract surgery will not be classified as AEs but will be recorded.

1. Snellen distance visual acuity (VA) by pinhole method
2. Slit lamp biomicroscopy
3. IOP measurement
4. Dilated ophthalmoscopy
5. Change from baseline (1-day post-surgery) to each post-surgery visit in ocular signs:
 - Conjunctival hyperemia
 - Corneal Edema

All Relevant clinical findings will be recorded in the electronic case report form (eCRF).

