5.1.3 Visit 3: Day 1 (1-day post-surgery)

This visit should be scheduled to occur in the morning, if possible, to allow for QID dosing on Day 1 for randomized subjects. Perform the following assessments. Ocular assessments are to be performed on both eyes, unless otherwise noted:

- Subject-Rated Ocular Pain Assessment – prior to any other assessments
- Assessment of adverse events following subject rated ocular pain assessment. Changes that are expected due to uncomplicated cataract surgery will not be classified as AEs but will be recorded.
- Concomitant medication update
- Snellen Distance VA by Pinhole Method
- Slit-lamp biomicroscopy
- Intraocular pressure by Goldmann Applanation Tonometry
- Randomization: subjects that meet eligibility criteria ([section 1](#)) should be randomized to one of the treatment groups through the Interactive Web Response System (IWRS).
- [REDACTED]
- Dispensation of IP and Dosing Diary: the subject will receive one bottle from the study kit and will be instructed to self-administer the first drop prior to leaving the clinic, under the supervision of the unmasked personnel. The subject will be instructed to record this first dose and all subsequent doses in the dosing diary.
- 40 minutes \pm 10 minutes post IP administration the subject will be assessed for AEs in both eyes. If any AEs are reported at visit 3 that may be attributed to the IP, these should be handled by the unmasked personnel.
- The subject will be instructed to take the bottle home and administer the IP three more times that day. Following the day of this visit the subject will be instructed to begin using the drops four times a day and to continue for the duration of the study.

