7.3 ADVERSE EVENT DEFINITIONS

Adverse Event (AE): Any untoward medical occurrence associated with the use of an investigational product in humans, whether or not considered drug related.

Adverse Reaction (AR): any AE caused by a drug. Adverse reactions are a subset of all suspected adverse reactions where there is reason to conclude that the drug caused the event.

Suspected Adverse Reaction (SAR):

Any AE for which there is a reasonable possibility that the drug caused the AE. For the purposes of IND safety reporting, “reasonable possibility” means there is evidence to suggest a causal relationship between the drug and the AE. A SAR implies a lesser degree of certainty about causality than adverse reaction, which means any AE caused by a drug.

Unexpected: An AE or SAR is considered “unexpected” if it is not listed in the Investigator’s Brochure or is not listed at the specificity or severity that has been observed; or, if an Investigator’s Brochure is not required or available, is not consistent with the risk information described in the general investigational plan or elsewhere in the current application.

Life-threatening: An AE or SAR is considered “life-threatening” if, in the view of either the Investigator or sponsor, its occurrence places the patient or subject at immediate risk of death. It does not include an AE or suspected adverse reaction that, had it occurred in a more severe form, might have caused death.

A SERIOUS ADVERSE EVENT (SAE) is any AE or suspected adverse reaction occurring at any dose that:

- Results in death.
- Is life-threatening.
- Results in a persistent or significant incapacity or substantial disruption of the ability to conduct normal life functions.
- Requires inpatient hospitalization.
- Prolongs inpatient hospitalization.
- Is a congenital anomaly/birth defect.
- Is a significant medical event (i.e., one that may jeopardize the subject or may require intervention to prevent one or more of the other outcomes listed above).

A NON-SERIOUS ADVERSE EVENT is any AE that does not meet the definitions for SAEs as described above.

Each **AE** will be classified as **SERIOUS or NON-SERIOUS** using the definitions provided above.

The **SEVERITY** of each AE will be classified as **MILD, MODERATE, or SEVERE**.

The Investigator will review each event and assess its **RELATIONSHIP** to use of investigational product (unrelated, probably, definitely). The AE will be assessed using the following definitions:

Unrelated:

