- Event occurring before dosing.
- Event easily explained by uncomplicated cataract surgery
- Event or intercurrent illness due wholly to factors other than investigational product use.

Probable:

- Reasonable temporal relationship with investigational product use.
- Likely to be known reaction to agent or chemical group, or predicted by known pharmacology.
- Event cannot easily be explained by subject's clinical state or other factors.

Definite:

- Distinct temporal relationship with investigational product use.
- Known reaction to agent or chemical group, or predicted by known pharmacology.
- Event cannot be explained by subject's clinical state or other factors.

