9.1.2 Analysis of Safety

Analysis of safety data will be presented for all subjects. AEs will be coded using Medical Dictionary for Regulatory Activities (MedDRA, most current version) and categorized by system organ class using preferred terms. Treatment emergent AEs will be listed by study group. Treatment related AEs will be tabulated by study group and will be reported by incidence (both number of events and number of subjects) with respect to their intensity and relationship to the IP. Ophthalmoscopy findings will be summarized descriptively. IOP measurements, VA, and slit lamp biomicroscopy will be summarized as safety outcomes.

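### The exclusion of changes expected after cataract surgery continues after the first study drop with no pre-dose reference, so the AE-based primary safety parameter is likely to under-count local symptoms

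*Combined protocol and SAP*

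**What the plan says.** Section 3.1 sets the endpoint: "The primary safety parameter in this study is the incidence and severity of treatment-emergent and treatment-related adverse events (AEs", both systemic and ocular. It then attaches a general exclusion: "Changes that are expected due to uncomplicated cataract surgery will not be classified as AEs but will be recorded". The synopsis, the visit descriptions in sections 5.1.3 to 5.1.6 and footnote 7 of Appendix 1 repeat the exclusion.

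Section 3.3, item 3.1 under Visit 3, applies it after dosing. At 40 ± 10 minutes "post first dose, AEs, if any, will be recorded", but the expected surgical changes are carved out, with these examples: "discomfort, scratchy feeling, significant brightness, changes in the perception of the operated eye, corneal edema) will be collected, but will not be classified as AEs".

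Section 7.3 defines an AE without any such carve-out: "Any untoward medical occurrence associated with the use of an investigational product in humans, whether or not considered drug related". Its causality scale, however, lists among the grounds for calling an event unrelated: "Event easily explained by uncomplicated cataract surgery".

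On analysis, section 9.1.2 says "Treatment related AEs will be tabulated by study group and will be reported by incidence", while treatment-emergent AEs are listed by group. IOP, visual acuity, slit-lamp and ophthalmoscopy findings are summarised. No summary is named for changes that are recorded but are not AEs. Section 9.1 promises listings of all study data by treatment, subject and visit.

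**The concern.** Several of the named examples are also how irritation from an eye drop would present. The rule turns on whether a change is expected from surgery. It does not ask whether the change was there before the drop, began after it, or became worse. An investigator who follows it as written can set aside a scratchy eye that was comfortable before dosing.

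The primary objective is safety compared with vehicle, and the primary safety parameter is built on AEs. If local symptoms are set aside, AE counts fall in every arm and the absolute gap between a dose and vehicle shrinks with them. A dose-related rise in instillation symptoms could then be hard to see in the AE tables, although the randomised vehicle arm had the same surgery and could supply the background rate.

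**Working it through.** The plan gives no AE rate that could be reproduced, its sample-size text is redacted, and the significance level is deferred to a SAP whose text is not supplied. The check therefore has two parts: what is captured where, and an illustration of scale.

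**1. What is captured outside the AE count**

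| Type of change | Other capture | What is left open |
|---|---|---|
| Conjunctival hyperemia, corneal edema | Change from Day 1 to each visit (synopsis, 3.1); graded 0–3 (Table 4); summarised (9.1.2) | On Day 1 the slit-lamp examination precedes the first dose (8.1), so there is no grade at 40 minutes |
| Lid hyperemia, lid edema, chemosis, discharge | Graded 0–3 (Table 4), summarised | As above |
| Discomfort, foreign-body sensation, stinging | Pain scale grade 1 (8.1.3); change from Day 1 on Days 3, 8 and 15, compared descriptively with vehicle (9.1.3) | Exploratory efficacy measure; not repeated at 40 minutes (Appendix 1); at Day 15 taken with that day's dosing withheld (5.1.5) |
| Brightness, altered perception | No symptom scale; visual acuity is summarised | No by-arm summary of the symptom |

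In Appendix 1 the AE assessment is the only item in the post-dose column of Visit 3. The exclusion therefore weakens the one scheduled check on immediate tolerability. Section 5.1.3 also has a pre-dose check on the same day ("Assessment of adverse events following subject rated ocular pain assessment"), so a pre-dose reference point exists but the rule does not use it.

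**2. Internal consistency**

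Section 3.3 says corneal edema of the expected kind is not an AE. Section 7.2.1 gives corneal edema as an example of an AE that need not be reported as serious. The AE definition in section 7.3 is broader than the exclusion. The three places do not say which governs when edema or a symptom appears after dosing. The unrelated category in section 7.3 adds a second filter: a symptom that is recorded as an AE can still be left out of the treatment-related table, the only AE table that section 9.1.2 names.

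**3. Scale**

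Inputs: about 60 subjects at 1:1:1:1 (synopsis), so 60/4 = 15 per arm. Assumptions, not taken from the documents: the true share p of subjects with local intolerance, and the share f of those whose event is set aside as expected, taken as equal in both arms.

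- Chance that an arm shows at least one such AE: 1 − (1 − p(1 − f))^15. For p = 0.20 and f = 0.5 this is 1 − 0.90^15 = 0.794; for f = 0.8 it is 1 − 0.96^15 = 0.458.
- Expected subjects with an AE: 15 × p × (1 − f).

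| f | At least one AE, p = 10% | At least one AE, p = 20% | Expected subjects, 40% vs 10% | Difference |
|---|---|---|---|---|
| 0 | 79.4% | 96.5% | 6.0 vs 1.5 | 4.5 |
| 0.5 | 53.7% | 79.4% | 3.0 vs 0.75 | 2.25 |
| 0.8 | 26.1% | 45.8% | 1.2 vs 0.3 | 0.9 |
| 0.9 | 14.0% | 26.1% | 0.6 vs 0.15 | 0.45 |
| 1.0 | 0% | 0% | 0 vs 0 | 0 |

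The counts and their difference fall in proportion to 1 − f. The signal disappears only in the last row, where every event is set aside.

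**The case against.** The exclusion covers changes due to surgery, which can be read as a judgement of attribution, not as a list of complaint types. On that reading a new post-drop complaint is not expected and stays an AE. Section 3.3 provides for AEs at the 40-minute check, so some post-drop events must qualify. Sections 3.3.3, 4.3.1 and 5.1.3 send AEs that may be attributed to the product to unmasked staff. Ocular signs are graded whatever their AE label, the pain scale covers part of the discomfort, and with about 15 subjects per arm a listing by treatment can be read by eye.

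Much of this stands. A reader might infer that listed complaints are barred even when they start or worsen after dosing, and that the trial cannot show local intolerance. The documents support neither. The first is an inference from silence, because expected is undefined and no text addresses onset or worsening. The second overlooks the graded signs, the pain scale and the reactions not expected from surgery, which remain AEs.

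What does not stand is that the gap is closed. The sections on unmasked staff do not say that attribution to the product overrides the exclusion. The attribution reading leaves each investigator to decide without a rule. A listing is not a by-arm summary.

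It is also fair to object to reclassifying every new or worsened change as an AE. Steroids and NSAIDs are withheld around surgery and eyes enter with cells of grade 2 or more, so that step would mix the surgical course and lack of efficacy into the safety counts. Section 6.2 keeps these apart when it says that need for rescue is not an AE.

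**Conclusion.** The point holds as an under-count, not as blindness to intolerance. The exclusion operates after the first drop and at every later visit without reference to the pre-dose state, and no by-arm summary of the set-aside changes is named. The gap is mainly in symptoms: immediate post-drop discomfort or scratchiness, brightness and altered perception.

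Its size cannot be fixed from the documents. Under the assumed 20% rate and 15 per arm, the chance of at least one AE in a dose arm falls from 96.5% to 79.4% or 45.8% when 50% or 80% of events are set aside. An AE table of zero against zero, which a reader might take as the outcome of the rule, is only the limiting case. These figures rest on assumed rates and on an equal set-aside share across arms; that share could differ if staff who know the assignment make the judgement. A table of these changes may exist in the SAP text that is not supplied.

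**What to change.** - In section 9.1.2, add a descriptive table by arm and visit, including the 40-minute check, of all recorded expected changes: number and percent of subjects, split into those present at the pre-dose Day 1 assessment and those new or worse after the first dose. Present it against vehicle beside the AE table.
- Wherever the exclusion appears (synopsis, 3.1, 3.3, 5.1.3 to 5.1.6, Appendix 1 footnote 7), define expected relative to the pre-dose Day 1 assessment.
- Reconcile section 3.3 with section 7.2.1 on corneal edema and with the AE definition in section 7.3.

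The cost is one descriptive table, some wording, and more reported local symptoms in every arm, including vehicle. The changes are already to be recorded before and after the first dose. The split also needs onset and severity for them; section 7.4 requires these for AEs, but the protocol does not say so for the set-aside changes, so the eCRF should be checked.

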3.3.1 Investigational product kit

3.3.2 Treatments administered

Eligible subjects for Tarsius 2020 Trial will be randomized in a 1:1:1:1 ratio to receive sterile ophthalmic solution of TRS01 [REDACTED], TRS01 [REDACTED]%, TRS01 [REDACTED]% or vehicle during the 14-day Treatment Period. All doses will be administered as eye drops in the inferior conjunctival fornix. Unmasked study personnel will train subjects on drop use during the screening visit.

Subjects will be asked by unmasked study personnel to dose with the drops prior to leaving the clinic on Day 1. Subjects will be advised to gently shake the IP bottle before instillation and to dose approximately every four hours during the day (example: first dose- 8:00am, second dose – 12:00pm, third dose - 4:00pm and fourth dose - 8:00pm). To increase assurance of IP delivery, subjects will be instructed to repeat a dose if they feel they did not effectively dispense adequate IP into their study eye. Every daily application of the drug will be recorded in the subject's dosing diary.

3.3.3 Method to minimize bias

In order to prevent unmasking during the study, the three doses of TRS01 and the vehicle will be supplied in identical packages.

Treatment assignments during the treatment period will be masked to all Tarsius staff, subjects and investigators, except delegated unmasked site personnel. The designated unmasked site personnel should collect all AEs related to IP and will handle all IP related responsibilities but will not perform any study related assessments.

The first dose will be administered under the supervision of an unmasked staff member and will serve as confirmation that the subject was adequately trained on drop administration at the screening visit. In the event that it becomes necessary to unmask a specific subject's treatment assignment, the Principal Investigator will contact Tarsius Medical Officer or the back-up Medical Officer. Unmasking will be allowed for individual subjects after it is determined necessary by the Medical Officer and the Principal Investigator, thus leaving the masking of the remaining subjects intact

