4.3.1 Masking and Randomization Methodology

Eligible subjects will be randomized in a 1:1:1:1 ratio to receive TRS01 [REDACTED], TRS01 [REDACTED], TRS01 [REDACTED] % or vehicle dose on Day 1.

Randomization will occur after subjects meet all eligibility requirements at Screening and Day 1/Visit 3 (1-day post-surgery). Each subject will be assigned a unique subject number.

Each kit package (containing two IP bottles) will contain a kit number that can be later correlated to the subject number at the site.

Randomization for the US sites will be separate from the French site.

The randomization codes and all data sets will be stored in a secure area accessible only to delegated study personnel and only released on completion of the study and after the study database has been locked.

In this study all parties are to be masked to the allocated treatment; investigators, study staff and subjects. At the site, there will be designated unmasked study staff that will train the subject on all study procedures related to IP administration.

In emergency situations for reasons of subject safety (e.g. serious unexpected /unlisted drug related event; medical emergency; potentially life-threatening drug interaction) the masking code may need to be broken. In those cases, whenever possible, a request for unmasking should be discussed with the sponsor (or designee) prior to unmasking. Detailed instruction on the method for breaking the mask will be provided during site training and noted in the Investigator study file.

Following the first IP administration, if the subject perceives any AE that may be attributed to the IP, these should be reported to the unmasked site personnel.

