5.1.5 Visit 5: Day 8 (± 1 day) post surgery

Perform the following assessments. Ocular assessments are to be performed on both eyes, unless otherwise noted:

- Subject-Rated Ocular Pain Assessment – prior to any other assessments
- Assessment of adverse events. Changes that are expected due to uncomplicated cataract surgery will not be classified as AEs but will be recorded.
- Concomitant medication update
- Slit-lamp biomicroscopy
- Snellen Distance VA by Pinhole Method
- Intraocular pressure by Goldmann Applanation Tonometry
- [REDACTED]
- Collect used IP and review subject's dosing diary for compliance by unmasked personnel
- Dispense second bottle of IP from subject's assigned kit by unmasked personnel. Subject should be reminded to withhold dosing on the day of Visit 6.

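### Sections 3.3 and 4.3.1 mask all site staff, but 3.3.3 exempts product-handling staff who meet subjects from Visit 3 to Visit 6, and the visible text shows no need for them to know the arm

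*Combined protocol and SAP*

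**What the plan says.** Section 3.3 masks everyone, site staff included: "Treatment assignments will be masked to Tarsius, study subjects, Investigators, and site staff". Section 4.3.1 says the same: "In this study all parties are to be masked to the allocated treatment; investigators, study staff and subjects". Section 3.3.3 then carves out an exception: "Treatment assignments during the treatment period will be masked to all Tarsius staff, subjects and investigators, except delegated unmasked site personnel". Section 4.3.1 does likewise in the sentence after its own blanket statement: "At the site, there will be designated unmasked study staff that will train the subject on all study procedures related to IP administration".

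The role of these staff is spread over several sections:

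- **Screening (3.3.2):** "Unmasked study personnel will train subjects on drop use during the screening visit".
- **Visit 3 (5.1.3):** the subject is "instructed to self-administer the first drop prior to leaving the clinic, under the supervision of the unmasked personnel". AEs at that visit that may be due to IP go to the same staff.
- **General (3.3.3):** they collect IP-related AEs and handle everything concerning IP, but are not to carry out study assessments.
- **Visits 4 to 6 (5.1.4 to 5.1.6):** they review the diary (at Visit 5, "dosing diary for compliance by unmasked personnel"), exchange the bottle at Visit 5, and collect IP and diary at Visit 6.

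**The concern.** A member of site staff cannot be both masked and excepted from masking. A site, a monitor or whoever configures the Interactive Web Response System (IWRS) cannot tell from these sections whether any site user should see the arm.

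The role also involves direct contact with subjects. Section 3.1 makes the incidence and severity of AEs the primary parameter, and section 7.4 has AEs elicited by open questions to the subject. Pain is subject-rated (8.1.3). Both can shift with tone, prompting or reassurance from someone who knows the treatment. The planned comparisons are descriptive and the arms are small, so a few events elicited differently by arm could alter the apparent dose pattern.

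**Working it through.** No figure in the plan bears on this point, so the check compares sections and counts contacts.

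**1. Is there a contradiction?** Sections 3.3 and 4.3.1 include site staff and study staff among the masked, with no exception. Section 3.3.3 excepts delegated site personnel, and what they are excepted from is masking of treatment assignments. Section 4.3.1 also names unmasked study staff. The conflict therefore lies between sections and within 4.3.1.

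**2. Does the visible text show a need to know the arm?**

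- Packages are identical across arms (3.3, 3.3.3).
- Vehicle subjects receive the same bottles, and a matching vehicle is prepared for masking (1.1).
- Kits carry a number that is linked to the subject number (4.3.1).
- Allocation is through the IWRS (5.1.3).
- Emergency unmasking has its own route through the Medical Officer or sponsor (3.3.3, 4.3.1).
- Drop training at screening precedes randomization, so no assignment exists to be known.

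None of these tasks needs the arm.

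**3. Which ratings could be reached?** Pain is rated before any other assessment (5.1.3 to 5.1.6; Appendix 1, note 4). Diary and IP tasks come last in the lists for Visits 4 to 6.

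| Visit | Contact with unmasked staff | Contacts since randomization before that visit's pain rating |
|---|---|---|
| 3 (Day 1) | First dose supervised, IP dispensed, IP-attributed AEs handled | 0 (rated before randomization) |
| 4 (Day 3) | Diary review | 1 |
| 5 (Day 8) | Diary review, bottle exchange | 2 |
| 6 (Day 15) | IP and diary collected | 3 |

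There are four contacts after randomization, but only those at Visits 3, 4 and 5 precede a later pain rating. Baseline pain is unaffected.

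**4. AEs.** Section 3.3.3 gives collection of IP-related AEs to these staff and in the same sentence bars them from assessments. Appendix 1 lists AE assessment as a scheduled item. Collecting AEs for the primary parameter is hard to square with doing no assessments.

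**5. Scale.** About 60 subjects at 1:1:1:1 gives 60 / 4 = 15 per arm. One subject more or fewer with an event moves an arm's incidence by 1 / 15, or 6.7 percentage points. This shows how sensitive the comparison is; it does not estimate bias.

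**The case against.** **Unmasked may be a role label.** No section says how these staff learn the arm or that the IWRS displays it to them, and the term is used for training done before any assignment exists. This stands as a doubt about actual knowledge. It does not remove the conflict, because 3.3.3 refers to treatment assignments in terms. If only a label is meant, the wording still needs correcting.

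**A reason may lie in text we cannot see.** Section 3.3.1 has no visible body and parts of 1.1 are redacted. The protocol promises identical packages and the same bottles, but does not say that the solutions look alike. This stands: a reader might infer that there is no reason for the role, and the documents support that only for the visible text.

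**Safeguards exist.** Section 3.3.3 bars these staff from assessments. Severity and causality rest with the Investigator (7.2.1, 7.4), who is masked. One investigator scores cells and flare throughout for a given subject (8.1.1). These protect grading and attribution, but not elicitation, since the investigator can judge only events that were raised and recorded. Rating pain first limits cues within a visit but not carry-over from earlier visits.

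**Code release.** Section 4.3.1 says codes are "only released on completion of the study and after the study database has been locked", which might be read as ruling out any earlier knowledge. The same sentence allows access by delegated study personnel, so it does not clearly conflict with 3.3.3.

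**Per Protocol set.** A reader might infer that arm-aware diary review distorts this set. Section 9.6 has the clinical study team and biostatistician define it before lock and unmasking. No section makes diary compliance a significant deviation, and 9.1 assigns no analysis to the set. The documents do not support that inference.

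**Conclusion.** The contradiction is real and should be resolved. Sections 3.3 and 4.3.1 state a broader mask than 3.3.3 applies, and the excepted staff meet every randomized subject from Visit 3 to Visit 6. AE elicitation, and pain ratings at Visits 4 to 6 after one to three earlier contacts, are open to cues from someone who may know the arm. All of about 60 randomized subjects are concerned. The size of any bias cannot be derived from the documents.

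Two stronger readings are not supported. One is that the trial is not double-masked: under 3.3.3 itself, subjects, investigators and the sponsor remain masked, so what fails is the claim that site staff and all other parties are. The other is that unmasked staff give the drops: they supervise the first dose, and the subject or a care provider instils it (3.3, 5.1.3).

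The conclusion assumes that 3.3.3 means what it says about assignments and that no removed text explains the exception.

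**What to change.** Reconcile sections 3.3, 3.3.3, 4.3.1 and 5.1.3 to 5.1.6, and the matching terms in 3.3.2, to state that:

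- staff who handle IP are separate from those who assess subjects;
- they work from the IWRS kit number only and are not shown the assignment;
- codes are held by the IWRS and the randomization holder until database lock, except for emergency unmasking.

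The staff now called unmasked should then be renamed.

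If the solutions are visibly different, so that handlers cannot be fully masked, the protocol should say so, correct the blanket statements in 3.3 and 4.3.1, and have masked staff elicit and record all AEs.

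The cost is wording changes, an IWRS role setting that hides the arm from site users, and the need to keep handlers apart from assessors at each site. Sample size, visits and endpoints do not change.
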